1. SYMPTOMS**PRESENCE/SEVERITY**

	Right	Left
a. Pain, aching, or burning in feet, legs:		
b. "Pins and needles" in feet, legs:		
c. Numbness (lack of feeling) in feet, legs:		
d. Total points (add a + b +c):		

AT SCREENING, THE DIFFERENCE BETWEEN LEGS SHOULD BE \leq 5 POINTS IN ORDER TO BE ELIGIBLE.

Adverse Event	An adverse event (AE) is the development of an untoward medical occurrence or the deterioration of a pre-existing medical condition following or during exposure to an investigational product, whether or not it is considered causally related to the product.
Baseline	The last non-missing value prior to first dose of study drug.
Serious AE	Any untoward medical occurrence which results in death; is a life-threatening experience; requires hospitalization (admission to hospital with a stay > 24 hours) or prolongation of an existing hospitalization which is not specifically required by the protocol or is elective; Results in permanent impairment of a body function or permanent damage to a body structure; or requires medical or surgical intervention to preclude permanent impairment of a body function or permanent damage to a body structure

1. INTRODUCTION

This document outlines the statistical methods to be implemented during the analyses of data collected within the scope of ViroMed Co., Ltd. Protocol VMDN-002 [A Phase II, Double-Blind, Randomized, Placebo-Controlled, Multi-center Study to Assess the Safety and Efficacy of VM202 in Subjects with Painful Diabetic Peripheral Neuropathy]. The purpose of this plan is to provide specific guidelines from which the analysis will proceed. Any deviations from these guidelines will be documented in the clinical study report (CSR).

2. OBJECTIVES

2.1. Primary Objective

The primary objective of this analysis is to evaluate the safety of IM administration of VM202 in subjects with painful diabetic peripheral neuropathy (DPN) in lower extremities 0.

2.2. Secondary Objectives

The secondary objective of the study is to evaluate potential bioactivity of intramuscular (IM) administration of VM202 in subjects with painful DPN in lower extremities, when compared to placebo, on:

- The average 24-hour pain score (obtained from the Daily Pain and Sleep Interference Diary) from baseline to the 6-month follow-up
- Visual Analogue Scale for Pain (VAS)
- Brief Pain Inventory for Diabetic Peripheral Neuropathy (BPI-DPN)
- Michigan Neuropathy Screening Instrument (MNSI)
- Patients' Global Impression Change (PGIC)
- The average 24-hour pain score interfering with sleep (obtained from the Daily Pain and Sleep Interference Diary)

The mean and mean change from baseline of these efficacy endpoints will be compared between the VM202 groups and the placebo group.

It should be noted that, in addition to the outcomes above, the evaluation of histological findings on skin biopsy will be provided by an independent lab.

3. STUDY OVERVIEW

This is a 9 month Phase II, double-blind, randomized, placebo-controlled, multi-center study designed to assess the safety and efficacy of VM202 in subjects with painful DPN.

Patients who meet the eligibility criteria will be randomized in a 2:2:1 ratio to one of three treatment arms: Low Dose (16 mg VM202), High Dose (32 mg VM202) or placebo (normal saline), respectively.

Patients in the Low Dose Group (16 mg VM202) will receive:

- Day 0: 4 mg of VM202/calf (16 injections of 0.5 ml of VM202/calf) and 16 injections of 0.5 mL of normal saline/calf.
- Day 14: 4 mg of VM202/calf (16 injections of 0.5 ml of VM202/calf) and 16 injections of 0.5 mL of normal saline/calf.

Patients in the High Dose Group (32 mg VM202) will receive:

- Day 0: 8 mg of VM202/calf (32 injections of 0.5 ml of VM202/calf)
- Day 14: 8 mg of VM202/calf (32 injections of 0.5 ml of VM202/calf)

Patients in the placebo control group will receive 32 injections/calf of 0.5 ml normal saline at each visit.

Table 1 lists the final dose and dose per visit to be administered by each study arm.

Table 1. VM202 administration for each study arm

TREATMENT GROUP	DOSE VM202 (mg) / VISIT / LEG		FINAL DOSE VM202 / LEG (mg)	FINAL DOSE VM202 / PATIENT (mg)
	DAY 0	DAY 14		
Low Dose	4	4	8	16
High Dose	8	8	16	32
Placebo	0	0	0	0

0 indicates injections of normal saline only

The schedule of study visits and the clinical parameters that will be measured at the visits are summarized in Table 2 below.

TABLE 2 SCHEDULE OF EVALUATIONS AND VISITS

Procedure	Screening / Baseline (-60 – 0 D)	1 st Injection Day 0		2 nd Injection Day 14 ± 1 D		Day 21 ± 3 D	Day 30 ± 3 D	Day 60 ± 3 D	Day 90 ± 7 D	6 months ± 1 mo	9 months ± 1 mo	Early Withdrawal
		Pre-dose	Post-dose	Pre-dose	Post-dose							
Baseline Evaluation												
Informed Consent	✓											
Complete Medical History	✓											
Complete Physical Exam	✓											
Cancer screening [†]	✓											
Viral screening – HIV, HTLV, HBV, HCV	✓											
Urinalysis	✓											
EKG	✓											
Pregnancy test	✓											
Safety and Efficacy Parameters												
VAS	✓	✓					✓	✓	✓	✓	✓	
MNSI ^{††}	✓									✓	✓	
Symptoms of BPNS	✓									✓		
Retinal Fundoscopy	✓										✓	✓
Daily Pain and Sleep Interference Diary	✓								✓	✓	✓	
Concomitant Medications	✓	✓		✓		✓	✓	✓	✓	✓	✓	✓
Vital Signs	✓	✓	✓	✓	✓	✓	✓	✓	✓	✓	✓	✓
PGIC *							✓	✓	✓	✓	✓	
BPI-DPN **		✓					✓	✓	✓	✓	✓	
Serum Chemistry and Hematology	✓	✓					✓		✓		✓	✓
HbA1c	✓								✓	✓	✓	✓
Serum HGF		✓		✓			✓	✓	✓			✓ ¹
Copies of VM202 in whole blood		✓	✓***	✓	✓***	✓	✓	✓	✓			✓ ¹
Skin biopsy		✓								✓		
Treatment												
Injection site reaction assessment			✓	✓	✓	✓	✓	✓	✓			✓ ²
Adverse Events			✓	✓	✓	✓	✓	✓	✓	✓	✓	✓

[†] Cancer screening: chest X-ray or chest CT scan if subject has a previous history of tobacco use within 3 months; pap smear and mammogram within past 12 months (females only); PSA within past 3 month (males only); for subjects ≥ 50 years old, colonoscopy within past 10 years; for subjects with a first degree relative with colon cancer, colonoscopy within past 12 months.

^{††} MNSI - Michigan Neuropathy Screening Instrument

1. If withdrawal occurred before Day 90 Visit

2. If withdrawal occurred before Day 60 Visit

* PGIC - Patient's Global Impression of Change

** BPI-DPN - Brief Pain Inventory, diabetic neuropathy specific test

*** 2 hours after injection (± 1 hour)

4. SAMPLE SIZE JUSTIFICATION

The sample size for this Phase 2 study was chosen to estimate effect sizes and variability for a pivotal study. Based on the 12 subjects in the Phase I study (Protocol VMDN-001), the overall mean VAS reduction from baseline to 6 months is about 23 mm with a standard deviation of about 25 mm.

This Phase II study has two VM202 dose groups (16 mg and 32 mg) and a placebo group. The study goal is to identify any difference in mean reduction in pain as measured by the Daily Pain and Sleep Interference Diary between each of the two VM202 groups against the placebo group. Based on the two-sided two-sample t-test with a significance level of 0.025 (per the Bonferroni adjustment for multiple comparisons) and an assumption of a standard deviation of 25 mm, a sample size of 40 subjects versus 20 subjects has a statistical power of 80% to detect a mean difference of 21.5 mm, a statistical power of 70% to detect a mean difference 19.5 mm, and a statistical power of 60% to detect a mean difference of 17.5 mm. Therefore, the sample size for Protocol VMDN-002 is determined to be 40 subjects in the VM202 16 mg group, 40 subjects in the VM202 32 mg group, and 20 subjects in the placebo group.

5. GENERAL ANALYSIS CONSIDERATIONS

The statistical analyses will be reported using summary tables, figures, and data listings. Continuous variables will be summarized with means, standard deviations, medians, minimums, and maximums for each treatment arm. Categorical variables will be summarized by counts and by percentage of subjects in corresponding categories.

All analyses and tabulations will be performed using SAS[®] Version 9.2 or higher on a PC platform.

It should be noted that this Phase II study is for planning the future Phase III studies, therefore the p-values of the statistical tests should be used descriptively with clinically interpretation.

5.1. Visit Windows

Data at each scheduled follow up visit will be analyzed according to the nominal visit identified on the CRF, regardless of the actual elapsed time since treatment.

5.2. Statistical Methods

Although the detectable effect size for the mean pain score reduction is calculated by the two-sided t-test with a significance level of 0.025 per Bonferroni adjustment, the Analysis of Variance (ANOVA) will be performed to detect any difference in the 6-month mean pain score reduction (as measured using the Daily Pain and Sleep Interference Diary) among the three study groups first and, if there is a significant findings based on ANOVA,

the Dunnett's test for the multiple comparisons will be used to compare each of the two VM202 groups and the placebo group in the 6-month mean pain score. Therefore, two-sided p-values <0.05 will be considered statistically significant, unless otherwise stated. As described previously, regardless of the statistical significance, the p-values of the statistical tests should be used descriptively with clinically meaningful interpretation.

Separate statistical tests will be performed at each time point for key endpoints of interest such as Visual Analogue Scale for Pain, Brief Pain Inventory for Diabetic Peripheral Neuropathy, Michigan Neuropathy Screening Instrument, Patients' Global Impression Change, and the [REDACTED] No adjustment for multiplicity will be performed.

In general, an overall test to determine if there is a statistically significant difference among the three treatment arms will be conducted first. Further comparisons will be made to determine if either the low or high dose groups are statistically significantly different from the placebo group.

For continuous variables, a one-way analysis of variance (ANOVA) with treatment group (high dose, low dose, and placebo) as a factor will be used to determine if there is a significant difference among the groups. The low and high dose groups will each be compared against the placebo group using Dunnett's test. The mean difference between the VM202 groups versus placebo along with 95% confidence intervals for the mean difference will also be presented.

For categorical variables, Fisher's exact test will be used to determine if there is a significant difference among the three treatment groups. Separate Fisher's exact tests will be used to compare the low and high dose groups to the placebo group.

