11.1. Primary Efficacy Analysis

Subjects will be asked to assess the level of pain they feel by selecting a score from 0 (No Pain) to 10 (Worst Possible Pain) in the 7-Day Daily Pain and Sleep Interference Diary 7 days before the Baseline, Day-90, 6-Month, and 9-Month Visits. The average of the pain score will be calculated for each subject at each visit.

The primary efficacy endpoint is the change in average pain score as determined by the 7-Day Daily Pain and Sleep Interference Diary between baseline and the 6-month follow-up. The change in pain will be calculated for each subject as follows:

$$\text{Change} = 6\text{-month Pain Score} - \text{Baseline Pain Score}$$

The baseline pain score is the average of average score at screening and at Day 0. Since higher scores indicate worse pain, a negative value of change means an improvement, and a positive value of change means deterioration.

The mean change in pain will be compared among the three treatment groups. The statistical null and alternative hypotheses for the primary efficacy endpoint are:

$$\begin{aligned} \text{Ho: } \mu_H &= \mu_L = \mu_P \text{ and} \\ \text{Ha: } &\text{at least one of the three } \mu \text{'s is different,} \end{aligned}$$

where μ_H , μ_L , and μ_P are mean change in pain from baseline to 6-month follow-up for VM202 high dose, VM202 low dose, and placebo groups, respectively.

The one-way Analysis of Variance (ANOVA) with treatment (VM202 high dose, VM202 low dose, and placebo) as the factor will be used to compare the mean change in pain among the three treatment groups. Dunnett's test will be used to compare the mean change in pain score between VM202 high dose to placebo and between VM202 low dose to placebo. The 95% confidence interval of the mean pain score difference between VM202 groups and placebo group will be provided.

The mean score and mean score change from baseline to Day-90, and 9 Months will also be summarized using the statistical methods described above.

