11.4. Multiplicity Adjustments

There will be no adjustments for multiple comparisons or interim analyses.

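### SAP 5.2 makes Dunnett's test on the primary endpoint conditional on a significant ANOVA, while later text and SAP 11.1 do not; the condition is not needed for error control and costs some power

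*SAP*

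**What the plan says.** SAP 4 sets the goal as finding a difference in mean diary pain reduction "between each of the two VM202 groups against the placebo group". It sizes each comparison by a two-sided t-test at 0.025. SAP 5.2 acknowledges that this differs from the planned analysis, so the sizing is not part of the conflict.

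The planned analysis is described in four places:

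- **SAP 5.2, first paragraph** (specific to the 6-month diary score): ANOVA first, then Dunnett's test "if there is a significant findings based on ANOVA".
- **SAP 5.2, later paragraphs** (general): an overall test first, then "Further comparisons will be made to determine if either the low or high dose groups are statistically significantly different from the placebo group". The rule for continuous outcomes reads: "The low and high dose groups will each be compared against the placebo group using" Dunnett's test. Neither sentence carries a condition.
- **SAP 11.1** (primary efficacy analysis): the null hypothesis is equality of all three means, tested by one-way ANOVA. Dunnett's "test will be used to compare the mean change in pain score between VM202 high dose to placebo", and likewise for the low dose, again with no condition. A 95% confidence interval for each difference is promised, without saying whether it is simultaneous.
- **SAP 11.4**: "There will be no adjustments for multiple comparisons or interim analyses". This is not limited to endpoints other than the primary.

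SAP 5 adds that "the p-values of the statistical tests should be used descriptively with clinically interpretation", and 5.2 repeats the point. SAP 5.2 nevertheless sets a two-sided 0.05 threshold for significance.

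**The concern.** The SAP does not settle whether Dunnett results are produced and interpreted after a non-significant ANOVA. A statistician following the first paragraph of 5.2 would stop; one following 11.1 would go on. That choice should not be open after unblinding.

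The precondition also fits the goal poorly. Dunnett's test controls the familywise error for exactly the two dose-versus-placebo comparisons that SAP 4 names, so it needs no prior test. The F-test is also directed at high versus low dose, which is not part of that goal. When the two doses perform alike, that second degree of freedom is wasted and the F-test can miss what Dunnett's test would find.

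Two related gaps add to the ambiguity. SAP 11.4, read literally, rules out an adjustment that Dunnett's test makes. And an unadjusted interval printed beside a Dunnett p-value can contradict it.

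**Working it through.** **Inputs.** From SAP 4: group sizes 40/40/20, SD 25 mm, differences 21.5, 19.5 and 17.5 mm with stated power 80, 70 and 60%, per-comparison two-sided level 0.025. From SAP 5.2: two-sided 0.05 for the ANOVA and Dunnett's test. Power depends only on difference/SD, so the results carry over to the 0-10 diary score at the same ratios.

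**Step 1: reproduce SAP 4.** Standard error of a dose-placebo difference = 25 × √(1/40 + 1/20) = 6.847 mm. Noncentrality = difference/6.847 = 3.140, 2.848, 2.556. With 58 df and critical value t(0.9875) = 2.301, noncentral-t power is 79.7, 70.7 and 60.2%. The SAP's figures reproduce.

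**Step 2: critical values for the planned analysis.** Error df = 100 − 3 = 97. F critical value (2, 97 df) = 3.090. The correlation between the two dose-placebo contrasts is 40/(40 + 20) = 2/3, which gives a two-sided 5% Dunnett critical value of 2.218 by numerical integration.

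**Step 3: compare the two rules.** The three group means and the pooled variance were simulated, with at least 1,000,000 replicates per scenario. *Alone* means a dose is declared when |t| > 2.218. *Conditional* means that F > 3.090 is also required.

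No effect in any group: familywise error is 5.0% alone and 3.4% conditional. With one active dose, Dunnett's test alone rejects the inactive dose 2.9% of the time. Error control does not need the ANOVA.

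| Scenario | Measure | 21.5 mm | 19.5 mm | 17.5 mm |
|---|---|---|---|---|
| Equal doses | Per-dose power, alone | 82.0% | 73.5% | 63.3% |
| | Per-dose power, conditional | 80.1% | 70.8% | 60.0% |
| | Loss, points | 1.9 | 2.6 | 3.3 |
| | Loss for at least one dose, points | 3.8 | 5.2 | 6.5 |
| Second dose at half the effect | Better dose, alone | 82.0% | 73.5% | 63.3% |
| | Better dose, conditional | 78.6% | 69.2% | 58.4% |
| | Loss, points | 3.4 | 4.3 | 4.8 |
| One active dose | Loss, points | 0.2 | 0.4 | 0.7 |

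**Step 4: one dataset, two answers.** Take observed benefits over placebo of 16 and 11 mm with pooled SD 25 mm.

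- Weighted mean benefit = (40×16 + 40×11 + 20×0)/100 = 10.8.
- Between-group sum of squares = 40×5.2² + 40×0.2² + 20×10.8² = 3416.
- F = (3416/2)/625 = 2.73, p = 0.070. The first paragraph of 5.2 stops here.
- Better dose: t = 16/6.847 = 2.337, Dunnett p = 0.038. SAP 11.1 reports a significant dose.

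**Step 5: the intervals.** Simultaneous half-width = 2.218 × 6.847 = 15.2 mm. Unadjusted half-width = 1.985 × 6.847 = 13.6 mm. At an observed 14.5 mm, t = 2.118 and Dunnett p = 0.063, yet the unadjusted interval is 0.9 to 28.1 mm and excludes zero.

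**The case against.** The strongest reply is that nothing depends on these tests. P-values are descriptive, no success rule is attached to them, and differences with intervals are reported whatever the ANOVA shows. That stands, and it caps the importance of the point. It does not remove it: 5.2 keeps a significance threshold, the results are meant to guide Phase III planning, and the descriptive label does not say which interval is printed.

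It can also be said that 5.2 is not truly contradictory. Its first paragraph is the specific rule, and the later text is general and keeps the same order. That is a fair reading of 5.2 by itself. But SAP 11.1 is equally specific to the primary endpoint and omits the condition.

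ANOVA followed by Dunnett's test is valid, if conservative, and with equal doses it still delivers essentially the 80, 70 and 60% of SAP 4. This is true. The shortfall below those figures (at most 1.6 points) arises only in the half-effect scenario, which is an assumption of this review and not of the SAP.

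The three-group test does match the null hypothesis in 11.1, and Protocol 6.3.2 lists low versus high dose as a secondary comparison. A secondary comparison can be made on its own, however; it does not need to control access to the primary one.

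Finally, the sentence in 5.2 declining multiplicity adjustment closes a paragraph on other endpoints, and few readers would take 11.4 to cancel Dunnett's test. That is likely so, and the edit to 11.4 is tidying.

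**Conclusion.** The concern holds. SAP 5.2 (first paragraph) and SAP 11.1 give different rules for the same endpoint, and the ANOVA precondition adds no error control that the two dose-versus-placebo comparisons need. Its cost is modest: about 2 to 3 points of per-dose power with equal doses, 3 to 5 points for the better dose when the other has half the effect, and under 1 point when only one dose works. These figures assume 40/40/20 analysed, normal data with a common SD, and the effect-to-SD ratios of SAP 4. Importance is minor to moderate because the p-values are descriptive, but the rule should be settled before unblinding.

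**What to change.** - In SAP 5.2, delete the requirement of a significant ANOVA before Dunnett's test.
- In SAP 5.2 and 11.1, state in the same words that the primary analysis is Dunnett's two comparisons, high dose versus placebo and low dose versus placebo, at a familywise two-sided 0.05, whatever the ANOVA shows.
- Restate the 11.1 hypotheses as those two comparisons, and report the F-test descriptively.
- Specify Dunnett simultaneous 95% confidence intervals.
- Limit SAP 11.4, and the matching sentence in 5.2, explicitly to other endpoints and time points.

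The sizing in SAP 4 can stand. The cost is SAP wording before unblinding, with no change to sample size or data collection. If unadjusted intervals were intended, the simultaneous ones are about 1.6 mm wider on each side (15.2 − 13.6) at SD 25 mm.

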6.3.2. SECONDARY EFFICACY ENDPOINTS

Other secondary endpoints and evaluations will include:

- Difference in all clinical parameters measured (VAS, BPI DPN, MNSI, PGIC, average pain score and sleep interference score from the Daily Pain and Sleep Interference Diary) and histological findings on skin biopsy between the low dose and high dose groups at all time points
- Change between treatment arms and placebo in VAS score from baseline to Day 30, Day 60, Day 90, 6 months, and 9 months.
- Change in mean pain score from the Daily Pain and Sleep Interference Diary between treatment arms and placebo from baseline to Day 90, 6 months and 9 months.
- Change between treatment arms and placebo in mean MNSI score from baseline to 6 months and 9 months.
- Change between treatment arms and placebo in BPI-DPN from baseline to Day 30, Day 60, Day 90, 6 months, and 9 months.

- Change in PGIC between treatment arms and placebo at Day 30, Day 60, Day 90, 6 months, and 9 months.
- Change between treatment arms and placebo in histological findings on skin biopsy from baseline to 6 months

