11.3. Other Efficacy Variables

The analyses for the other efficacy variables will be performed based on the Efficacy Analysis Group unless specified otherwise. No imputation for the missing data will be performed for these efficacy endpoints. These efficacy endpoints include:

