11.3.1. VISUAL ANALOGUE SCALE FOR PAIN (VAS)

Subjects will be asked to assess the level of pain they feel by placing a perpendicular line on a scale of 0 (No Pain) to 100 mm (Very Severe Pain) at Day-0, Day-30, Day-60, Day-90, 6-Month, and 9-Month Visits at the clinic. This is a separate analysis from the 7-Day Daily Pain and Sleep Interference Diary. The subject's Visual Analogue Scale (VAS) score will be determined by where the subject places the perpendicular line. The average of the VAS measured by two readers will be calculated for each subject at each visit. The VAS measurements and change from baseline (average of VAS at screening and Day 0, or if data are missing from either, the value recorded at either visit will be summarized at each required visit by treatment arm using method for continuous variables.

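### In the ITT tables for VAS, BPI-DPN and sleep interference, a separate ANOVA at each visit leaves drop-outs' earlier scores unused at 6 and 9 months; a repeated-measures model would use them, for a small gain

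*SAP*

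**What the plan says.** SAP 5.2 sets the rule for the repeated secondary scales: "Separate statistical tests will be performed at each time point for key endpoints of interest such as Visual Analogue Scale for Pain". For continuous variables the model is "a one-way analysis of variance (ANOVA) with treatment group (high dose, low dose, and placebo) as a factor", followed by Dunnett's test of each dose against placebo. Across visits and scales, "No adjustment for multiplicity will be performed".

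SAP 11.3.1, 11.3.2 and 11.3.5 apply this method by visit to four scores:

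- **VAS**, collected "at Day-0, Day-30, Day-60, Day-90, 6-Month, and 9-Month Visits at the clinic", so five follow-up visits.
- **BPI-DPN severity and BPI-DPN interference**, also five follow-up visits each. Protocol 6.3.2 lists "Change between treatment arms and placebo in BPI-DPN from baseline to Day 30, Day 60, Day 90, 6 months, and 9 months" and, for VAS, "Change between treatment arms and placebo in VAS score from baseline to Day 30, Day 60, Day 90, 6 months, and 9 months".
- **Sleep interference**, from the diary, at three follow-up visits (Day 90, 6 months, 9 months; Protocol 3.2).

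On missing values, SAP 11.3 says: "No imputation for the missing data will be performed for these efficacy endpoints". The LOCF and maximum-value rules in SAP 11.1.1 cover only the primary endpoint in the ITT group.

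SAP 11.3 makes the Efficacy Analysis Group the default for these scales. SAP 6 and 11 add ITT analyses, and SAP Appendix A lists them as Tables 6.2, 7.2 and 10.2. Neither document contains a repeated-measures model or names a main visit for these four scores.

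**The concern.** With a one-way ANOVA at each visit and no imputation, a subject without a value at a visit drops out of that visit's comparison. The SAP does not say this in words, but it follows from the two rules together. A subject who leaves after Day 90 may have VAS and BPI-DPN scores at Days 30, 60 and 90 and a sleep score at Day 90. None of these informs the 6- or 9-month contrasts.

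Those earlier scores are the only efficacy data available after treatment for such subjects. The early-withdrawal assessments in Protocol 3.5.2 and Appendix 1 include no VAS, BPI-DPN or diary, and replacement under Protocol 3.5.2 covers only discontinuation before the Day 90 visit. Drop-out linked to pain is plausible, because Protocol 3.4.4.2 bars new drugs for DPN symptoms during the study and bars opioids until the 9-month visit.

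At stake are the precision and, under pain-related drop-out, the bias of the late ITT contrasts. SAP 4 says the trial was sized to estimate effect sizes and variability for a pivotal study, so estimation quality matters even where p-values do not.

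**Working it through.** **1. Planning inputs.** SAP 4 gives 40 against 20 subjects, SD 25 mm and two-sided alpha 0.025. The noncentral-t power (58 df) is 79.7%, 70.7% and 60.2% at 21.5, 19.5 and 17.5 mm, against the stated 80%, 70% and 60%. The figures reproduce, so SD 25 mm and 40/20 are used below.

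**2. Assumptions.** The documents give neither the between-visit correlation nor a drop-out rate. For illustration:

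- Correlation between visits is 0.7.
- Mean VAS change is -8 mm on placebo, and the true effect is -15 mm, constant over visits. The active mean is therefore -8 - 15 = -23 mm, the size of the Phase I mean reduction quoted in SAP 4.
- Drop-out after Day 90 is 40% if VAS did not improve by Day 90 and 5% otherwise.

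**3. Bias of the 6-month available-case contrast.** Let c = -mean/25. The chance of no improvement is P(Z ≥ c), and drop-out is 0.05 + 0.35 × P(Z ≥ c). Among those who stay, the mean 6-month change shifts by 0.7 × 25 × [-0.35 × φ(c) / (1 - drop-out)].

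| | c | P(Z ≥ c) | Drop-out | φ(c) | Shift at 6 months (mm) |
|---|---|---|---|---|---|
| Placebo | 0.32 | 0.374 | 18.1% | 0.379 | -2.83 |
| Active | 0.92 | 0.179 | 11.3% | 0.261 | -1.80 |

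The available-case contrast is -15 + (-1.80) - (-2.83) = -14.0 mm, a bias of 1.0 mm towards no effect. Simulation of this scenario agrees: about -14.0 mm for the per-visit ANOVA and -14.9 to -15.1 mm for a likelihood repeated-measures fit.

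**4. Sensitivity of the bias**, by the same formula:

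- Placebo change 0 instead of -8 mm: shifts -3.15 and -2.39, bias about 0.8 mm.
- 20% instead of 40% drop-out in non-improvers (0.15 replaces 0.35; placebo change -8 mm): shifts -1.11 and -0.74, bias about 0.4 mm.

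**5. Precision.** In the simulation of step 3 the SD of the estimated contrast is 7.5 mm for the per-visit ANOVA and 7.2 mm for the likelihood model. Total error is √(7.5² + 1.0²) = 7.6 mm against about 7.2 mm.

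A two-visit closed form gives the gain at one visit. With drop-out d, the variance factor is 1/(1-d) for available cases and 1 + [d/(1-d)](1-ρ²) for the likelihood analysis. At ρ = 0.7 the gain in effective sample size is 1.111/1.057 - 1 = 5% at d = 10%, and 1.250/1.127 - 1 = 11% at d = 20%. For ρ from 0.3 to 0.8 it is about 1% to 7% at d = 10% and 2% to 15% at d = 20%.

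**6. Efficacy Analysis Group.** SAP 6 requires the 6-month assessment for entry. Where every subject has the 6-month score, a model with treatment, visit, treatment-by-visit and unstructured covariance returns the same 6-month difference in means as the planned ANOVA. Any gain in that group is confined to other visits.

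**The case against.** The strongest reply is that this hardly matters. These are secondary endpoints in a phase II trial. SAP 5 and 5.2 say that p-values are to be read descriptively, and the primary endpoint is a single diary contrast at 6 months. The default population is nearly complete at 6 months. The severe drop-out pattern above is an assumption, and the trial programme gives little sign of it: Protocol 1.6.3 reports 12-month pain results for all 12 subjects in the earlier DPN study, and Protocol 1.6.2 reports two early withdrawals among 33 subjects in the critical limb ischaemia study. All of this stands, and it limits the point to the ITT tables and to about 1 mm or less.

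The reply does not remove the point. Descriptive p-values do not repair an estimate that ignores collected data.

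A reader might infer three stronger criticisms. The documents do not support them:

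- **A large precision loss.** The standard error of a five-visit average is √((1+4ρ)/5) times that of one visit, or 0.775 to 0.872 for ρ of 0.5 to 0.7, so 13% to 23% smaller. That average is a different estimand and needs an effect that is constant from Day 30. If the effect built up as 40, 60, 80, 100 and 100% of its full size, the average would be 76% of it. Signal-to-noise would be 0.76/0.775 = 0.98 to 0.76/0.872 = 0.87 of a single visit, and the gain is gone.
- **Dozens of wholly unadjusted p-values.** The dose comparisons use Dunnett's test, so they are adjusted for the two doses. Only adjustment across visits and scales is absent, and the SAP says so openly.
- **Visit-level comparisons that should not be there.** Protocol 6.3.2 lists them as secondary endpoints. Removing them would depart from the protocol.

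**Conclusion.** The point holds as a modest, low-cost improvement to the ITT analyses of four secondary scores. The per-visit ANOVA leaves out earlier post-treatment scores of subjects missing at 6 or 9 months. This costs some precision, and it biases those contrasts if drop-out depends on earlier pain.

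Under the severe pattern assumed here, the 6-month VAS bias is about 1 mm of 15 and the SD of the estimate falls from 7.5 to 7.2 mm. Under milder drop-out the bias is about 0.4 mm. These sizes rest on the assumed correlation, placebo change and drop-out rule.

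It would be wrong to conclude that the trial's main result is at risk. The primary endpoint is not analysed this way across visits and has its own missing-data rule in ITT. The 6-month contrast in the Efficacy Analysis Group is nearly unchanged. Nor do the scales ignore within-subject information altogether: they are analysed as change from baseline, so each subject's own baseline is used. What goes unused is the correlation among follow-up visits. Selection caused by requiring the 6-month assessment in the Efficacy Analysis Group is a separate matter that this change does not address.

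**What to change.** In SAP 5.2, 11.3.1, 11.3.2 and 11.3.5, before the randomization code is unmasked, specify the following for VAS, BPI-DPN severity, BPI-DPN interference and sleep interference, at least in the ITT group:

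- Fit one likelihood-based repeated-measures model per score to change from baseline, with treatment, visit and treatment-by-visit, unstructured covariance, and all available follow-up visits.
- From that model report each dose-placebo difference with its 95% CI at every visit listed in Protocol 6.3.2 (for sleep interference, the three diary visits). Name 6 months as the main visit and keep a Dunnett-type adjustment for the two doses. The model alone does not give one leading answer, so the main visit has to be named.
- Keep visit means and SDs as descriptive summaries.
- Treat a contrast averaged over visits as optional. If it is reported, label it as a different estimand that assumes a roughly constant effect.

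The cost is SAP wording and one standard model per score, with no new data or visits. The analysis then relies on data being missing at random given the observed scores, and on the covariance model. With five visits the unstructured form has 5 × 6 / 2 = 15 parameters from about 100 subjects, so a fallback structure should be stated in case the fit fails.
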